6.2 Estimation and Precision

Given the pilot nature of the study, emphasis will be put on estimation and precision of estimates, rather than null hypothesis testing. We will use large-sample methods (e.g., Wald CIs) when the nominal CI coverage level is tenable. Primary endpoints, which are evaluated only among the participants that received the MyChoice intervention, will be analyzed strictly descriptively with no formal hypothesis testing.

6.3 Multiplicity and Confidence Interval Coverage

An alpha of 0.05 will be used throughout analysis to compute 95% CIs, with no adjustment for multiplicity. In the case of analyses of continuous data with $n < 30$, 95% CI coverage properties of large-sample methods will be evaluated in simulation studies or existing exact statistical methods (e.g., exact CI for a risk difference) will be used.

6.4 Analysis Population and Approach

Acceptability, **appropriateness**, and **feasibility** endpoints will be restricted to women who were randomized to and participated in the MyChoice intervention. For the secondary outcome of decisional conflict, the SOC group will serve as the referent. Analyses will be conducted using an intention-to-treat (ITT) approach, analyzing participants according to their original randomization assignment.

6.5 Small Data

Appropriate descriptive statistics will follow standard formats (e.g., n (%), median (IQR), mean (SD) if subgroup size are small (e.g., <5 participants per category for categorical data or <10 participants in comparison group for continuous analyses), an exact 95% CI will be calculated as a sensitivity analysis. (e.g., exact CI for a risk difference).

6.6 Chance Imbalance

We anticipate that our measured baseline covariates will be balanced between the arms by randomization. However, if there is evidence of considerable chance imbalance in key baseline covariates, a **post hoc sensitivity analysis** may be conducted for the secondary outcome using **Augmented Inverse Probability Weighting (AIPW)** to adjust for these imbalances and can be used to produce double robust effect estimates compared to Inverse Probability of Treatment Weighting (IPTW). This analysis will be exploratory in nature and will not replace the unadjusted primary analysis. A doubly robust approach would also be suitable, if feasible, given our sample size (n=50 per arm). The protocol does not address chance imbalance, and such an analysis would be a sensitivity approach.

6.7 Missing Data

Missing (unevaluable) data are anticipated to be uncommon for the primary endpoints. Therefore, we will conduct a complete case analysis of the primary study endpoints, excluding participants that are missing all items pertaining to a given scale measure. We may also provide best-case, worst-case upper and lower bounds around our estimates in the case of >10% unevaluable data, assuming either all missing endpoints fall into the favorable (best-case) or unfavorable (worst-case) categories. Women who did not complete the 2-month visit will be excluded from the denominator of those primary endpoints assessed at that visit (AIM, IAM).

Among a given study arm for the secondary outcome (DCS), if >10% of participants in either randomization group are unevaluable, multiple imputation (MI) using chained equations (aka fully conditional specification [FCS] method) may be applied under a missing at random assumption (White 2011). Thirty or more MI datasets may be created, and results will be combined using Rubin's rule. Each imputation model will be specified prior to conducting outcome analyses by randomization group, and missingness patterns will be reviewed prior to finalizing imputation models. The imputation models will consider interaction terms between randomization group and covariates and will include at least all the covariates in the outcome analysis model; covariate values will also be imputed for the chained equations as needed. Interactions will be evaluated for inclusion only if sample size allows. Factors that are related to both the endpoint and to missingness will be important for inclusion in the imputation models.

6.8 Analysis Cohorts

- **Intention-To-Treat (ITT)**: all participants who are enrolled and randomly assigned to and received the MyChoice or SOC intervention.

7. Primary Outcomes

Acceptability, Appropriateness, and Feasibility Outcomes

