5.16.2 Analysis of secondary endpoints

Decisional Conflict

Decisional Conflict Scale (DCS) will be calculated according to published methods. A mean of the 16-item scale (rated on a 5-point scale) will be taken and multiplied by 25 to produce summary scores ranging from 0-100 points.^{71,74} Descriptively, summary scores will be presented descriptively (mean and SD across participants in each arm by study). We will compare DCS scores across in the SDM intervention condition to the SOC counselling control condition in an exploratory manner. We hypothesize that the intervention will be superior to the control, with intervention participants reporting at least an 8-point lower decisional conflict score on average than control participants. An intent-to-treat approach will be used to evaluate the effect of treatment on decisional conflict. We will first compare group means of decisional conflict scores by study arm and then examine the intervention's effect on this outcome using a two-sample Welch's t-test. If demographic variables related to decisional conflict differ substantively by study arm, we will instead use augmented inverse probability weights (AIPW) to perform doubly robust estimation of the average intervention effect to compare intervention vs. control (e.g., using the CAUSALTRT procedure in SAS software). Missing (unevaluable) data are anticipated to be uncommon ($\leq 10\%$). Multiple imputation methods will be applied to address missing data if appropriate.

Exploratory analyses will also be conducted with a dichotomous coding of DCS score according to published thresholds. A "low" DCS score will be identified using a cut-off of 25 out of 100, which has been linked to reduced decisional regret and enhanced choice retention. DCS scores will be computed based on women's responses to statements, where higher scores indicate greater decisional conflict, while lower scores indicate diminished conflict and heightened certainty in decision-making.

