5.16.3 Quantitative analysis of exploratory endpoints

We will examine the intervention effect on retention and PrEP adherence in an exploratory fashion. In order to evaluate effectiveness, analyses will be conducted using an intention-to-treat approach, with women analysed according to the arm they were randomly assigned.

Given the pilot nature of these studies, emphasis will be put on estimation and precision of measured effects, rather than null hypothesis testing. An alpha=0.05 will be used throughout to compute 95% confidence intervals (CIs), with no adjustment for multiplicity. In the case of small cell counts (<5), 95% CI coverage properties of large-sample methods will be evaluated using exact statistical methods (e.g., exact CI for a risk difference) in sensitivity analyses. Given potential for precision loss with exact CI methods and the pilot nature of these studies, we will use large-sample methods (e.g., Wald CIs) when the nominal CI coverage level is tenable.

Missing (unevaluable) data are anticipated to be uncommon ($\leq 10\%$). The primary analyses are based on a composite endpoint of being retained in care with functional PrEP use, and thus complete case analyses will be conducted. Women who are not retained in care will be counted in the denominator for the primary analysis. Sensitivity analyses will exclude women who were not retained in care.

PrEP uptake

Uptake of oral PrEP will be described as the proportion of participants with record of receipt of an oral PrEP prescription.

Retention + Functional Adherence

Our clinical exploratory endpoint to be measured among participants taking up PrEP is retention in care with functional adherence to PrEP at two months. We will assess adherence to oral PrEP among participants taking it up through Tenofovir diphosphate (TFVdp) concentrations in participant dried blood spot (DBS) samples. TFVdp will be measured using

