8.3 Cohort and Study Arm

Secondary outcomes will be assessed only among participants randomized to both the MyChoice Intervention and SOC arm using ITT.

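### SAP 6.8 labels as intention-to-treat a set that requires receipt of counselling, and the 10% missing-data rule for decisional conflict does not say whether uncounselled women count

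*SAP*

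**What the plan says.** **The cohort.** SAP 6.8 lists one cohort, called Intention-To-Treat: "all participants who are enrolled and randomly assigned to and received the MyChoice or SOC intervention". No other set is defined.

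**The stated principle.** SAP 6.4 says: "Analyses will be conducted using an intention-to-treat (ITT) approach, analyzing participants according to their original randomization assignment". Protocol 5.16.2 says of the secondary outcome: "An intent-to-treat approach will be used to evaluate the effect of treatment on decisional conflict". Protocol 5.16.3, writing about the exploratory endpoints, explains the term as "with women analysed according to the arm they were randomly assigned". None of these sets a receipt condition for DCS.

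**Where the cohort is used.** SAP 8.3 reads: "Secondary outcomes will be assessed only among participants randomized to both the MyChoice Intervention and SOC arm using ITT". SAP 7.4 also uses the ITT label for the primary outcomes, although SAP 6.4 says that those "endpoints will be restricted to women who were randomized to and participated in the MyChoice intervention".

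**Missing data.** For DCS, SAP 6.7 allows multiple imputation "if >10% of participants in either randomization group are unevaluable", and SAP 8.5(iv) repeats the rule. For the primary endpoints SAP 6.7 offers: "We may also provide best-case, worst-case upper and lower bounds around our estimates in the case of >10% unevaluable data". Both provisions are optional.

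**The concern.** An intention-to-treat set is fixed at randomisation. Receipt of counselling is decided afterwards, by staff and participants, and Protocol 5.7.2 says that staff are not blinded. A set that depends on receipt no longer has the full protection of randomisation, and the DCS comparison is where that protection is needed.

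Two consequences follow from the wording.

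- **Undefined receipt.** Protocol 5.2 lets a MyChoice participant defer or decline the decision, or ask for a second session, possibly with a partner. Protocol 5.3 describes no such option for standard of care. The SAP does not say whether a partial or deferred session counts as receipt. A woman in that position who has a DCS could be kept or dropped by a judgement made with her arm known.
- **Uncounted losses.** If the 10% rule is worked out within the 6.8 cohort, a randomised woman who was not counselled is not recorded as unevaluable. She is simply absent, and the SAP asks for no count of such women.

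**Working it through.** **Inputs from the documents.** 50 women randomised per arm (SAP 4.2); DCS SD 13.26 (Protocol 5.15.1); trigger of more than 10% unevaluable in either group (SAP 6.7, 8.5(iv)); DCS given at month 0 after counselling (SAP 8.4); at least one completed item needed for analysis (SAP 8.5(ii)).

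**Assumption.** The number of non-recipients in an arm, k, is not given. I use 0 to 10.

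**Step 1: the plan's own figure.** Protocol Table 7 gives a by-arm half-width of ±3.768 at baseline. The formula t(0.975, n−1) × SD/√n with n = 50 and SD = 13.26 gives 3.768, which matches. The planned precision therefore takes all 50 randomised women per arm as evaluable. No stated figure is in dispute.

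**Step 2: the passages side by side.** SAP 6.4 and Protocol 5.16.2 require randomisation and analysis by assigned arm. SAP 6.8 requires randomisation and receipt. SAP 8.3 sends DCS to the ITT cohort, and 6.8 is the only definition of that cohort. The two rules give different sets as soon as one randomised woman is judged not to have received counselling.

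**Step 3: the 10% rule under each denominator.** Let m be the number of recipients with no DCS item.

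- All randomised: triggered when (k + m)/50 > 0.10.
- Within the 6.8 set: triggered when m/(50 − k) > 0.10.

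| k | m needed, all randomised | m needed, 6.8 set | Largest true loss with the 6.8 rule silent |
|---|---|---|---|
| 0 | 6 | 6 (of 50) | 5/50 = 10% |
| 1 | 5 | 5 (of 49) | 5/50 = 10% |
| 2 | 4 | 5 (of 48) | 6/50 = 12% |
| 4 | 2 | 5 (of 46) | 8/50 = 16% |
| 6 | 0 | 5 (of 44) | 10/50 = 20% |
| 10 | 0 | 5 (of 40) | 14/50 = 28% |

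Two examples:

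- Six non-recipients and no other loss: 6/50 = 12% against 0/44 = 0%.
- Four non-recipients plus two missing scores: 6/50 = 12% against 2/46 = 4.3%.

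The trigger is the same under both denominators for k = 0 and k = 1. It differs from k = 2 upwards.

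**Step 4: what the definition does not change.** Take five non-recipients without a DCS and no other missing scores. With all randomised women counted, 5/50 = 10%, which is not above 10%, so the rule is not met. SAP 8.5(ii) then leaves the same 45 women in the analysis under either definition, and the estimate is identical. The definition alters the estimate only if it removes a woman who has a score, or if imputation is triggered and actually used.

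**The case against.** The strongest reply is that the two sets may coincide. Randomisation and counselling both belong to the enrolment visit, and SAP section 5 has the assigned counselling given once the randomisation number is issued. DCS is a secondary outcome, compared in an exploratory way in a pilot that stresses estimation. This stands and limits the size of the problem. It does not remove the contradiction between 6.8 and 6.4.

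A second reply is that the 10% rule speaks of randomisation groups and does not cite 6.8, so it may already mean everyone randomised. That is a fair reading. But 8.3 places the whole DCS analysis in the 6.8 cohort, so the other reading is also open. What the documents support is an unstated denominator, not a certainty that non-recipients are hidden.

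A reader might go further in three ways that the documents do not support.

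- **A DCS bias of some number of points caused by 6.8.** No source gives a rate of non-receipt or a difference in scores. DCS follows counselling, so a non-recipient will normally have no score under either definition (step 4). Imputation under missing at random would not in general recover an unobserved difference.
- **Inflated acceptability.** Restricting AIM, IAM and FIM to recipients is deliberate and is stated in Protocol 5.15.2 and SAP 6.2, 6.4 and 7.6. A woman cannot rate counselling that she did not receive. The fault there is the ITT label in 7.4.
- **More walk-outs because MyChoice takes longer.** Neither document gives a session length for either arm. The deferral and second-session provisions are the only documented difference of this kind.

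**Conclusion.** The point holds as a definitional error that should be corrected before outcome analysis. SAP 6.8 makes a post-randomisation event a condition of the cohort called ITT, contradicts SAP 6.4 and Protocol 5.16.2, and through 8.3 governs the SAP's only between-arm outcome comparison. Because receipt is undefined, women with an observed DCS could be excluded with the arm known.

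The effect on the 10% rule is conditional. It arises if the rule is applied within the 6.8 set and at least two women in an arm are non-recipients. With six non-recipients, true loss could reach 20% of an arm before the rule responds. Even then imputation is only permitted, not required. The documents give no non-receipt rate, and the timing of counselling suggests that it will be low. No numerical bias in the DCS difference can be claimed from the documents.

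**What to change.** 1. In SAP 6.8, define ITT as every randomised woman, analysed in her assigned arm whether or not she was counselled.
2. In SAP 6.7 and 8.5(iv), state that the denominator of the 10% rule for DCS is all women randomised to the arm, and that a woman with no DCS counts as unevaluable.
3. Keep the restriction of AIM, IAM and FIM to recipients, but give that set its own name, such as MyChoice recipients, and use the name in 7.4 in place of ITT. State what counts as receipt for that set.
4. Report the number randomised but not counselled in each arm.

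The cost is SAP wording and one count per arm. No new data, visits or participants are needed. A few women may be shown as unevaluable who would otherwise have been left out without a count.

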7.1 Acceptability Endpoint (a)

- (i) AIM acceptability scale mean score for the MyChoice intervention at **months 0 and 2**, respectively.

7.2 Appropriateness Endpoint (b)

- (i) IAM appropriateness scale mean score for the MyChoice intervention at **months 0 and 2**, respectively.

7.3 Feasibility Endpoints (c)

- (i) FIM feasibility scale mean score for the MyChoice intervention at **month 0**

For **all** primary outcomes, the **month 0** visit will be the primary result for each endpoint. For **acceptability** and **appropriateness** measures, **month 2** result will serve as the supplemental result.

7.4 Cohort and Study Arm

These outcomes will be assessed only among participants randomized to the MyChoice intervention arm using ITT.

7.5 Measures

All primary outcomes will be assessed through participant self-report in the SDM Intervention Acceptability and Appropriateness instrument using the following standardized instruments (Appendix B):

- (a) **Acceptability** will be measured using the **Acceptability of Intervention Measure (AIM) scale**.
- (b) **Appropriateness** will be measured using the **Intervention Appropriateness Measure (IAM) scale**.
- (c) **Feasibility** will be measured using the **Feasibility of Intervention Measure (FIM) scale**.

Each scale consists of four items rated on a 5-point Likert scale coded from 1 to 5 with 1 representing “completely disagree” and 5 representing “completely agree”, corresponding to increasing levels of (a) acceptability, (b) appropriateness, or (c) feasibility, respectively. During implementation coding was reversed, such that 1 corresponds to “completely agree” and 5 to “completely disagree”.¹ To maintain consistency with the original published scales, items will be reversed coded prior to calculating a mean scale score. Each of these questions includes a non-response option, coded as 999. This will be set to missing for calculating summary scores. Each

participant's summary score for a given scale will be calculated as the **mean** of the non-missing item responses. Summary scores will range from 1 to 5, with higher scores indicating more favorable perceptions of the intervention.

- (a) The items used to assess MyChoice intervention **acceptability** at month 0 and month 2 consists of the four-item AIM scale rated on a 5-point scale¹. After reverse coding (see above), each item will range from 1= "completely disagree" to 5= "completely agree," so that higher scores reflect increasing acceptability. At least one item among the four must be completed to calculate an acceptability score for a participant.
- (b) The items used to assess MyChoice intervention **appropriateness** at month 0 and month 2 consist of the four item IAM rated on a 5-point scale¹. After reverse coding, each item will range from 1= "completely disagree" to 5= "completely agree" so that higher scores reflect increasing appropriateness. At least one item among the four must be completed to calculate an appropriateness score for a participant.
- (c) The items used to assess MyChoice intervention **feasibility** at month 0 consists of the four-item FIM scale rated on a 5-point scale¹. After reverse coding, each item will range from 1= "completely disagree" to 5= "completely agree," so that higher scores reflect increasing feasibility. At least one item among the four must be completed to calculate a feasibility score for a participant.

7.6 Analysis

- (i) **Item-Level Summary:** Among participants that received the MyChoice intervention, we will describe the distribution of responses for each individual item within the **acceptability** (a) and **appropriateness** (b) and **feasibility** (c) scales. For **acceptability** and **appropriateness**, we will summarize responses at **month 0** and **month 2**, separately. For **feasibility** (c), we will describe the distribution of responses to each of the question items at **month 0**, as this construct was not assessed at Month 2. Descriptive statistics will include counts, percentages, and graphical summaries were appropriate.
- (ii) **Scale-Level Summary:** We will then calculate a mean score for each participant that received the MyChoice intervention at each applicable time point. Across participants at each time point, we will estimate the mean of these individual means the common standard error using the sum of squared differences between the individual and population means, and the 95% CI around the sample mean for each construct (acceptability, appropriateness, feasibility). These calculations will be performed separately for **month 0** and **month 2**. Participants with at least one or more completed item on a given scale will be included in these analyses. We will calculate the weighted group mean where we weight the mean for each participant by the inverse of their individual variance and get a pooled SE (square root of the sum of individual variance estimates divided by the N²)

The formula is as follows:

Weighted mean of means (\bar{x}_w) where each participant i 's variance ($Var(\bar{x}_i)$) from their individual mean \bar{x}_i is multiplied by their individual mean (\bar{x}_i) and summed across all participants N and then divided by the sum of the variance for participants $i = 1$ to N .

$$\bar{x}_w = \frac{\sum_i^N w_i \bar{x}_i}{\sum_i^N w_i}, \quad w_i = \frac{1}{Var(\bar{x}_i)}$$

Pooled standard error

$$(SE_{pool}): \sqrt{\frac{1}{N^2} \sum_i^N Var(\bar{x}_i)}$$

(iii) **Descriptive Comparisons Over Time:** Although the study is not powered to detect statistically significant within-subject changes, we will describe observed changes in mean scale scores for acceptability and appropriateness from **Month 0** to **Month 2** to provide insight into potential shifts in participant perceptions over time.

8. Secondary Outcomes

Decisional Conflict Scale

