5.16.1 Analysis of primary endpoints

Descriptive statistics will be calculated for primary outcomes of intervention acceptability, appropriateness, and feasibility among intervention arm participants. For each 4-item scale, item scores will be averaged to produce a composite score for each participant (range 1-5). Higher scores will indicate a greater level of acceptability, appropriateness, or feasibility, respectively. We will estimate the mean differences between arms for each primary outcome with a corresponding 95% confidence interval and p-value.

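### SAP 7.6(ii) adds an inverse-variance weighted mean to each primary outcome; it cannot be computed if any woman answers all items alike, and the SAP does not say which mean is reported

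*SAP*

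**What the plan says.** SAP 7.5 scores each four-item scale as the average of whatever items a woman answered, on a range of 1 to 5. One answered item is enough; for feasibility the wording is "At least one item among the four must be completed to calculate a feasibility score for a participant", and the other two scales have the same rule.

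SAP 7.6(ii) then gives two summaries across women.

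- **First estimator.** The average of the individual means, with "the common standard error using the sum of squared differences between the individual and population means, and the 95% CI around the sample mean". On inclusion it says: "Participants with at least one or more completed item on a given scale will be included in these analyses".
- **Second estimator.** "We will calculate the weighted group mean where we weight the mean for each participant by the inverse of their individual variance". The printed weight is the reciprocal of the variance of the woman's own mean. The verbal description above the formula instead has the variance multiplying the mean, with the total "divided by the sum of the variance for participants". A pooled standard error is given as the square root of the summed individual variances over N².

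SAP 7.3 says that the month 0 "visit will be the primary result for each endpoint", but does not name an estimator. SAP 6.2 says the primary endpoints "will be analyzed strictly descriptively with no formal hypothesis testing". Protocol 5.16.1 has no weighting across women; it says only that "item scores will be averaged to produce a composite score for each participant".

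**The concern.** These are the study's three primary outcomes, and SAP section 6 puts the emphasis on estimation and precision. A programmer following 7.6(ii) would produce two point estimates and two standard errors per construct, with no rule on which is the result.

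Inverse-variance weighting also does not suit these data. The variance being inverted is the scatter of one woman's answers across at most four items. Weighting by it favours women who answer consistently, whatever their view of the counselling, and breaks down for a woman whose answers are all identical. With four similarly worded items (SAP Appendix B), identical answers are an ordinary response pattern. Any repair, such as dropping these women or putting a floor under the variance, would have to be chosen after the data were seen, and it changes the estimate.

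**Working it through.** **Inputs.** From the documents: 50 women in the MyChoice arm and 45 at follow-up after 10% loss; SD 0.9 for participant mean scores (protocol 5.15.1); four items scored 1 to 5; the formulas in SAP 7.6(ii). The documents give no item-level data, so all response patterns and within-woman SDs below are assumptions.

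**Notation.** m_i is woman i's mean score, s_i² the variance of her item answers, and V_i the variance of her mean. For four items V_i = s_i²/4; a programmer might instead use s_i².

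**1. Reproduce protocol Table 6.** Half-width = t(0.975, n−1) × 0.9/√n.
- n = 50: 0.2558, printed as ±0.256.
- n = 45: 0.2704, printed as ±0.270.

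The normal quantile would give 0.249 and 0.263, so Table 6 is the t interval for the unweighted mean.

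**2. Weights, w_i = 1/V_i.**
- Answers 5,5,5,4: s² = 0.25, V = 0.0625, w = 16.
- Answers 5,5,5,5: V = 0, so w = 1/0, undefined.
- One answered item: the n−1 variance is 0/0. With divisor n it is 0, and the weight is again 1/0.

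One such woman is enough to make the printed weighted mean fail, and no rule covers the case.

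**3. Formula against verbal description (constructed example A).** 25 women answer 5,5,5,4 (mean 4.75, s² = 0.25) and 25 answer 2,4,2,4 (mean 3.00, s² = 1.333).
- Unweighted: (4.75 + 3.00)/2 = 3.875; SD 0.884; half-width 0.251.
- Printed formula, weights proportional to 4 and 0.75: (4 × 4.75 + 0.75 × 3)/4.75 = 4.474.
- Verbal description, weights 0.25 and 1.333: (0.25 × 4.75 + 1.333 × 3)/1.583 = 3.276.

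All three means are the same under either reading of V.

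**4. Pooled SE, √(ΣV_i/N²).** It contains only item scatter within women.
- Example A: 0.063 (V = s²/4) or 0.126 (V = s²). The usual SE of an inverse-variance mean, 1/√Σw, is 0.046 or 0.092, so the pooled SE does not match the weighted mean either.
- Constructed example B (25 women all 5s, 25 all 3s): SD 1.010, so the unweighted result is 4.00 ± 0.287 (2.010 × 1.010/√50). Every V_i is 0, so the weighted mean is undefined and the pooled SE is exactly 0.
- If the pooled SE were used for an interval at n = 50 (multiplier 1.96), within-woman SDs of 0.3 to 0.9 would give half-widths of 0.042 to 0.125 with V = s²/4. With V = s² the range is 0.083 to 0.249, and 0.277 at SD 1.0. The planned figure is 0.256.

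**5. A high-scoring pattern (assumed).** 20 women all 5s, 12 with 5,5,5,4, 8 with 5,5,4,4, 6 all 4s, 4 with 2,3,3,4. 26 of 50 have no finite weight.

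| Estimate | Value |
|---|---|
| Unweighted mean (SE) | 4.58 (0.081) |
| Weighted, 26 women dropped | 4.54 |
| Weighted, V floored at 0.01 | 4.74 |
| Weighted, V floored at 0.0001 | 4.77 |
| Verbal description | 4.11 |
| Pooled SE | 0.029 |

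**6. Simulation (assumed latent means 3.5 to 4.5, between-woman SD 0.9 to 1.2, item SD 0.3 to 0.8; n = 50).** Between 9% and 57% of women had zero variance. The unweighted SE was 2.15 to 4.35 times the pooled SE. With zero-variance women dropped, the average weighted mean differed from the average unweighted mean by +0.01 to −0.33 points.

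**The case against.** The best defence is that the first estimator is plainly the intended one. SAP 7.1 to 7.3 define each endpoint as a scale mean score, the only 95% CI in 7.6(ii) is attached to the sample mean, and the protocol uses no weighting. A descriptive plan may also report two summaries. This supports the choice of fix, but the SAP still commits to the second calculation without giving its status.

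Several qualifications stand:

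- For a woman with uniform answers it is the weight, and so the weighted mean, that is undefined. The pooled SE still computes, but she adds zero to it. For a single-item responder the pooled SE also fails if the n−1 variance is used.
- Under the verbal version a uniform responder simply gets weight zero, and the mean exists unless every woman is uniform.
- The inclusion sentence comes before the weighted mean and might be read as governing only the first estimator. Nothing in the SAP excludes these women from the second.
- Example A is extreme. The simulated shifts are smaller and mostly in the opposite direction, so neither the size nor the sign of the shift in the real data can be known from the documents.
- 1/√Σw is itself valid only for known variances and a common mean, and neither holds here.
- The first estimator is not fully specified: 7.6(ii) names no divisor or quantile, and the large-sample intervals favoured in SAP 6.2 would give ±0.249 rather than ±0.256 at n = 50.

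None of this rescues the weighted mean as written.

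**Conclusion.** The concern holds: the second estimator in SAP 7.6(ii) is wrong as written. The undefined weight, the conflict between the verbal description and the formula, and the missing between-woman variation can all be read off the text and do not depend on any assumed data. The numerical sizes do: they rest on constructed response patterns and assumed within-woman SDs.

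This should be fixed, but it does not threaten the trial. The primary analysis is descriptive, the SAP does not attach an interval to the pooled SE, and the protocol 4.1 target (a score of at least 4 in at least 80% of participants) uses neither the weighted mean nor its SE. A reported interval would be wrong only if the pooled SE were used to build it.

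**What to change.** In SAP 7.6(ii), delete the weighted mean, its verbal description and the pooled SE. For each construct and visit, name one reported result: the unweighted mean of participant scale scores, the SD across participants, and the 95% CI as mean ± t(0.975, n−1) × SD/√n. The paragraph already largely describes this, and writing in the t quantile keeps it in line with protocol Table 6 (±0.256 and ±0.270).

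If the team wants to keep a weighted mean, it should be labelled supplementary, with a stated rule for zero or inestimable variance, a valid SE, and text that agrees with the formula.

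The cost is SAP wording only; there is less to program and no new data are needed. SAP 7.5 describes the item coding during implementation in the past tense, so data collection may already have begun. The change should therefore be a dated amendment that states whether outcome data had been seen.
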